11.1.1 Expectedness

An adverse event is considered "unexpected" if it is not listed in the investigator brochure, protocol, ICF, or is not listed at the specificity or severity that has been observed; or, if an investigator brochure is not required or available, is not consistent with the risk information described in the general investigational plan or elsewhere in the current application.

Anticipated adverse events for this study include: Pain, Bruising, Swelling, Edema, Allergy, Penile Fracture, and/or New Penile Curvature.

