4.1 Additional Study Sites

No additional study sites.

5. Study Population

15 males with ED of organic origin and diabetes. All patients will be regular PDE5i users/responders. Men with ED will be evaluated by IIEF-EF domain and eligible patients will be enrolled in this open label pilot study. Participants who do not meet eligibility criteria will be considered a screen failure and will not receive the study therapy.

5.1 Inclusion criteria:

In order to participate in this study, a patient must:

- 1) Be Male.
- 2) Be 30 to 80 years of age (inclusive).
- 3) Be able to provide written informed consent.
- 4) Have a diagnosis of mild to moderate ED (12-21) or mild ED (22-25) based on IIEF-EF questionnaire score.
- 5) Have diagnosis of Diabetes Mellitus (Type 1 or Type 2) as documented by history of hemoglobin A1C > 7% OR on medical therapy for Diabetes.
- 6) Be in a stable relationship and have a minimum of 2 sexual attempts per month for at least one month prior to enrollment.
- 7) Agree to comply with all study related tests/procedures.

5.2 Exclusion criteria:

In order to participate in this study, a patient must not have any of the following:

- 1) Previous penile surgery of any kind (except circumcision and condyloma removal), such as penile lengthening, penile cancer surgery, penile plication, grafting.
- 2) Previous history of priapism, penile fracture, Peyronie's Disease, or penile curvature that negatively influences sexual activity.
- 3) Abnormal morning serum testosterone level defined as a value lower than 300 ng/dL (±5%).
- 4) Psychogenic ED as determined by study investigator.
- 5) Patients using ICI for management of ED
- 6) Patients with generalized polyneuropathy, neurological conditions, or psychiatric disease (such as bipolar disorder or depression).
- 7) Have a serious comorbid illness or condition that, in the opinion of the investigator, may compromise the safety or compliance of the subject or preclude successful completion of the study.
- 8) History of consistent treatment failure with PDE5 inhibitors for therapy of ED.
- 9) Poorly controlled diabetes as indicated by Hemoglobin a1c > 7.5%.
- 10) Use of antiplatelet medication.

6. Identification and Enrollment of Subjects

6.1 Recruitment and Pre-screening

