7.2 Description of Study Procedures

- **7.2.1** *Informed Consent:* Refer to Section 6.3 for details regarding the informed consent process. Study procedures will be completed only after participants have signed the informed consent documentation.
- **7.2.2** *Demographics:* Demographic characteristics will be recorded including: date of birth, gender, marital status, race and ethnicity.
- **7.2.3** *Medical History:* Assessment of current and past medical, surgical, and social history will be conducted.
- **7.2.4** *Physical Examination:* Genitourinary/Reproductive system physical exam will be performed.
- **7.2.5 Doppler Ultrasound:** Penile Doppler ultrasound will be performed as standard of care for the management of erectile dysfunction. Results from within the past 12 months can be extracted from the medical record for use in this study.
- **7.2.6** *International Index of Erectile Function (IIEF) Questionnaire*: This validated 15-item self-evaluation scale provides pre and post treatment clinic evaluations of erectile function, orgasmic function, sexual desire, satisfaction in sexual intercourse and general satisfaction. If the subject has completed the IIEF questionnaire within the past 6 months, those results may be requested and used for the purpose of this research study. Questionnaires will be completed prior to therapy at injection visits.
- 7.2.7 Erectile Dysfunction Inventory of Treatment Satisfaction (EDITS) Questionnaire: This is a psychometrically sound questionnaire used to assess satisfaction with medical treatment modalities for erectile dysfunction.
- **7.2.8** *Visual Analogue Pain Scale (VAS)*: The visual analog scale (VAS) is a validated, subjective measure for acute and chronic pain. Scores are recorded by making a handwritten mark on a line that represents a continuum between "no pain" and "worst pain".
- **7.2.9** *Laboratory Testing:* Hematology, chemistry, hemoglobin A1C, and serum testosterone lab test results will be collected at screening. If any standard of care labs testing has been performed within 12 months of the date of the screening visit, those results may be used for the purpose of this study.

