7.3 Description of Study Visits

7.3.1 Screening Visit

Visit 1 (0 – 28 days before therapy): The basic work-up will take place, including medical and sexual history, as well as necessary lab tests (testosterone, prolactin, hematology, chemistry), if not available during the last 12 months prior to screening. Subjects will complete the IIEF questionnaire. We will ensure that patients have 4 attempts for intercourse Screening visit can occur on same day as first injection + SWT. Refer to table 1 for procedures to be performed at the Screening visit.

7.3.2 Treatment Visits: Week 0 – Week 4

Upon evaluation of eligibility, subjects will be randomized to one of the two parallel study groups using an online program, and initiate treatment on the same day.

There will be 5 treatment visits for all groups, each occurring at weekly intervals (\pm 2 days), for a total duration of five weeks. Subjects will complete a Visual Analogue Scale (VAS) pain score after the end of each treatment. Refer to table 1 for all procedures to be performed at the treatment visits.

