7.3.3 Follow Up Visits: Months 3 and 6 Post-Treatment

Follow up visits will occur within 90 \pm 14 days (Month 3) and 180 \pm 14 days (Month 6) days after final treatment visit. Refer to table 1 for procedures to be performed at the follow up visits visit.

8. Investigational Product

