11.1 Adverse Events (AEs)

An adverse event (AE) is defined as any untoward medical occurrence associated with the use of a drug in humans, whether or not considered drug related. An AE can be any unfavorable and unintended sign (including an abnormal laboratory finding), symptom, or disease temporally associated with the study. The event does not need to have a causal relationship with treatment. Common Terminology Criteria for Adverse Events Version 5 (CTCAE) will be used for describing AEs. All urological and/or reproductive system AEs will be recorded. For all other AEs, only events greater than grade 2 will be recorded.

Based on our own pilot data assessing SWT and PRP monotherapy, we have compiled the following data on adverse events (Table 2):

We anticipate there to be few adverse events related to the study. Based on the four published studies and abstracts, including 75 men, only minor adverse events were reported (Bruising 1, Mild Pain 4). No serious adverse events were observed [23-26].

SWT related adverse events	
Transient mild cutaneous purpura	0.10%
Local erythema	0.50%
Local swelling/edema	1.00%
Transient local anesthesia or paranesthesia	1.10%
Transient local anestnesia of paranestnesia	1.10/0

PPR related adverse events					
Pain greater than 5/10 at time of injection	5.00%				
Pain lasting > 5 days	5.00%				
Penile bruising	0.00%				
Penile fracture	0.00%				

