13.1 Risks to Subjects

We anticipate there to be few adverse events related to the study. Based on the four published studies and abstracts, including 75 men, only minor adverse events were reported (Bruising 1, Mild Pain 4). No serious adverse events were observed [23-26]. After literature review, we believe this product to be of non-significant risk to patients (NSR) and for investigational use in a clinical study protocol.

Based on published studies, we will record anticipated adverse events to patients include: local injection site reaction, penile pain, penile hematoma (bleeding into the tissue), penile swelling, allergic reaction to the anesthetic, local infection, penile fracture, or new penile curvature. In addition, there may be uncommon or previously unknown risks that might occur. We will record every adverse event at every visit systematically.

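### The genitourinary exam is scheduled only at screening and the adverse event review has no stated method, so anticipated penile events after treatment are found only by patient report or incidental observation

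*Combined protocol and SAP*

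**What the plan says.** Two lists name the local events that the protocol expects. Section 11.1.1 reads: "Anticipated adverse events for this study include: Pain, Bruising, Swelling, Edema, Allergy, Penile Fracture, and/or New Penile Curvature". Section 13.1 extends this to "penile hematoma (bleeding into the tissue), penile swelling, allergic reaction to the anesthetic, local infection, penile fracture, or new penile curvature". Haematoma and local infection appear only in the second list.

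Two commitments cover recording. Section 11.1 says "All urological and/or reproductive system AEs will be recorded", with no grade threshold, and its definition of an adverse event includes signs as well as symptoms. Section 13.1 says "We will record every adverse event at every visit systematically".

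The examination is defined in section 7.2.4: "Genitourinary/Reproductive system physical exam will be performed". The Schedule of Events in section 7.1 marks it once, in the screening column. The visit descriptions add nothing. For treatment visits, section 7.3.2 says "Refer to table 1 for all procedures to be performed at the treatment visits"; for follow-up, section 7.3.3 says "Refer to table 1 for procedures to be performed at the follow up visits visit". Adverse event review is marked at every visit from Day 0 to Month 6, but section 7.2.15 only points to section 11, which gives no method.

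**The concern.** The protocol undertakes to capture all urological events, names several that are physical findings, and then schedules no procedure to look for them once treatment has begun. Pain is handled differently: it has its own instrument, the VAS, at all five treatment visits. Curvature, plaque, haematoma and infection have none.

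Safety of the combination is part of the secondary objective (section 2.2). Mild curvature, early plaque or a resolving haematoma may not be mentioned by the man. If the final report says that no new curvature was seen, a reader will take it that someone looked. Under this schedule it would mean only that none was reported or happened to be noticed.

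Curvature is the sharpest case, because calling it new requires the same observation before and after treatment, and only the first of these visits has an exam.

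**Working it through.** The plan gives no figure to reproduce here, so the check sets the schedule beside the commitments and then measures the gaps.

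**Scheduled observation of the penis, from section 7.1 with sections 7.2 and 8.2**

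| Visit | Genitourinary exam | Adverse event review | Other penile contact |
|---|---|---|---|
| Screening | yes | no | Doppler |
| Week 0 (Day 0) | no | yes | injection, shockwave |
| Weeks 1, 2, 3 | no | yes | shockwave |
| Week 4 (Day 28) | no | yes | injection, shockwave |
| Month 3 (Day 90) | no | yes | none |
| Month 6 (Day 180) | no | yes | Doppler |

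From Day 0 onward the exam is marked at 0 of 7 visits and the adverse event review at 7 of 7.

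**Gaps after the second injection.** Inputs from the Schedule of Events: Day 28 ± 2, Day 90 ± 14, Day 180 ± 14.

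- To the next visit: 90 − 28 = 62 days. With windows, (90 − 14) − (28 + 2) = 46 to (90 + 14) − (28 − 2) = 78 days.
- To the next penile examination or imaging (the Month 6 Doppler): 180 − 28 = 152 days. With windows, (180 − 14) − 30 = 136 to (180 + 14) − 26 = 168 days.

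Section 7.3.3 counts the follow-up visits from the final treatment, which would make these gaps 90 ± 14 and 180 ± 14 days. The two passages need to be reconciled; the gap is long under either.

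**Whether the Month 6 Doppler fills the gap.** Its endpoint in section 3.2 is PSV and EDV; no curvature, plaque or haematoma reading is described. Section 7.2.5 also allows results from the past 12 months to be taken from the medical record and does not confine this to baseline.

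**Whether a baseline for curvature exists.** Section 7.2.4 names no curvature or plaque item. Section 5.2 excludes men with "Previous history of priapism, penile fracture, Peyronie's Disease, or penile curvature that negatively influences sexual activity". The final qualifier can be read as admitting men with milder curvature.

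**Scale, for illustration only.** With n = 15, true event rate p and detection probability s, the chance of recording at least one event is 1 − (1 − p·s)^15. The documents give neither p nor s; the values below are assumptions.

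| p | s = 1 | s = 0.8 | s = 0.5 |
|---|---|---|---|
| 1% | 14.0% | 11.4% | 7.2% |
| 5% | 53.7% | 45.8% | 31.6% |
| 10% | 79.4% | 71.4% | 53.7% |

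With perfect detection and 0 of 15 events, the exact one-sided 95% upper limit is 1 − 0.05^(1/15) = 18.1%. That limit comes from the sample size alone.

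**The case against.** The strongest reply is that the man's own report is not the only source. Adverse event review is scheduled at all seven visits from Day 0. Staff treat the penis directly at each of Weeks 0 to 4, so a visible haematoma, swelling or infection after the first injection could well be seen. A penile Doppler is marked at Month 6. This stands: a reader might infer that detection rests on self-report alone, and the documents do not support that. They do not say whether the review is by question, inspection or examination. But nothing requires staff to look for these events or to record that none was present, and hands-on contact ends at Week 4.

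A reader might also infer that the exclusion criteria guarantee a baseline free of curvature. They do not, for the reasons given in the working. Repeating the exam without adding curvature and plaque items at screening would therefore not settle what is new.

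It is also tempting to divide the 18.1% limit by a presumed detection rate and quote a much larger bound on the true rate. No document supplies that rate, so such a figure has no standing as a finding.

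Finally, the only safety endpoint listed in section 3.2 is serious adverse events, which mild curvature or a resolving haematoma would not ordinarily meet. Nor could 15 men in a single arm establish absence of structural change even with perfect examinations, and the protocol does not plan such a claim. Both points stand and limit the weight of the concern. They do not remove the mismatch between the recording commitments and the schedule.

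**Conclusion.** The concern holds in a limited form. No genitourinary exam is scheduled at any of the seven visits from Day 0, and the adverse event review has no stated method, although the protocol anticipates curvature, fracture, haematoma and infection and commits to recording urological events of every grade. The weakest stretch follows the second injection: 152 days by the schedule (136 to 168 with windows) without a planned penile examination or imaging, ending in a Doppler that is not described as a structural check.

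The likely result is under-recording of mild structural events. Its amount cannot be estimated from the documents. The conclusion assumes that the visits follow the protocol as written, with no unwritten clinic practice of examining at each visit. The serious adverse event endpoint is largely unaffected; what suffers is the safety objective and the all-grade urological commitment. This is a worthwhile, inexpensive improvement and not a flaw that invalidates the pilot.

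**What to change.** 1. In section 7.2.4, add plaque and curvature items to the screening exam so that a baseline is documented.
2. In the Schedule of Events, mark the section 7.2.4 exam at Week 4 (before the second injection), Month 3 and Month 6, with a short checklist: plaque, curvature, haematoma, swelling, signs of infection. State that it is done in person at the visit and not taken from the record. Compare it with screening and record any new finding as an adverse event.
3. In section 7.2.15 or 11.1, say how adverse events are ascertained at each visit, so that the promise of systematic recording in section 13.1 has a method behind it.
4. In section 7.2.5, say whether the 12-month allowance applies to the Month 6 Doppler.

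The cost is a few minutes at three existing visits, a slightly longer screening exam and one eCRF page. No new visit, invasive procedure or additional assessor is needed. The recorded adverse event rate may rise, because events that would otherwise pass unnoticed will be counted. The proposal concerns detection and recording only and leaves treatment decisions to the protocol.

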11.1.2 Severity

Common Terminology Criteria for Adverse Events, Version 5 (CTCAE v5.0) will be used to assess severity of adverse events. All grade 3-5 adverse events, regardless of association with the investigational therapy, will be entered into study database and reviewed at research committee meetings.

11.2 Serious Adverse Events (SAEs)

A serious adverse event (SAE) is defined as an AE which, in the view of the Investigator results in: 1) Death; 2) a life-threatening event (i.e. an event in which the subject was at risk of death at the time of the event; it does not refer to an event which hypothetically might have caused death if it were more severe); 3) inpatient hospitalization of > 24 hours or prolongation of existing hospitalization; 4) a significant disability/incapacity; or 5) a congenital anomaly/birth defect. Other important medical events may be considered SAEs if, in the opinion of the Investigator, they jeopardize the subject or require intervention to prevent one of the other outcomes listed above. Based on prior investigations, we do not anticipate any SAEs related to the study procedures [23-26].

11.3 Treatment Emergent Serious Adverse Events (TE-SAEs)

A treatment emergent serious adverse event (TE-SAE) is defined as any serious adverse event for which there is a reasonable possibility that the investigational product caused the adverse event. For the purposes of safety reporting, "a reasonable possibility" means there is evidence to suggest a causal relationship between the study product/procedures and the adverse event.

12. Statistical Considerations

12.1 Data Analysis Plan

Analysis plan: Continuous data will be analyzed using ANOVA with repeated measures, or student's T-Test (where applicable) in order to compare differences between the treatment and control groups. For categorical data, Fisher's Exact test to determine differences between groups. Statistical significance will be evaluated using α =0.05.

13. Risks and Benefits

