****CONFIDENTIAL & PROPRIETARY****

List of Abbreviations and Definition of Terms

AE	Adverse Events
BPH	Benign Prostatic Hyperplasia
BRB	Biomedical Research Building
CNS	Central Nervous System
CRF	Case Report Form
CTCAE	Common Terminology Criteria for Adverse Events
eCRF	Electronic Case Report Form
ED	Erectile Dysfunction
EDITS	Erectile Dysfunction Inventory of Treatment Satisfaction
EDV	End Diastolic Velocity
GCP	Good Clinical Practice
HIPAA	Health Information Portability and Accountability Act
ICF	Informed Consent Form
ICH	International Conference of Harmonization
ICI	Intracavernosal Injection
IEC	Institutional Ethics Committee
IIEF	International Index of Erectile Function
IIEF-EF	Erectile Function Subdomain Score
IRB	Institutional Review Board
ISCI	Interdisciplinary Stem Cell Institute
MCID	Minimal Clinically Important Difference
mL	Milliliter
ng/dL	Nanograms Per Deciliter
PDE5i	Phosphodiesterase 5 inhibitor
PPP	Platelet Poor Plasma
PRFM	Platelet Rich Fibrin Matrix
PRP	Platelet Rich Plasma
PSV	Peak Systolic Velocity
RCT	Randomized Controlled Trial
SAE	Serious Adverse Events
SEP3	Sexual Encounter Profile
SOP	Standard Operating Procedure
SWT	Low-intensity Shockwave Therapy
TE-SAE	Treatment Emergent Serious Adverse Events
UM	University of Miami
VAS	Visual Analogue Pain Scale

Protocol Synopsis						
TITLE	COMBINING SHOCKWAVE THERAPY AND PLATELET RICH PLASMA FOR TREATING ERECTILE DYSFUNCTION IN DIABETIC MEN (COCKTAIL-DM)					
SPONSOR	Jniversity of Miami, Miller School of Medicine - Department of Urology					
PHASE OF STUDY	Phase I/II					
STUDY THERAPY	Autologous Platelet-Rich Plasma (PRP) + Low-intensity Shockwave Therapy (SWT)					
STUDY DESIGN	Single arm, Open Label, Pilot Trial					
ROUTE OF ADMINISTRATION	Intracavernosal Injection (PRP) + extracorporeal shockwave therapy (SWT)					
SUBJECT POPULATION	15 male subjects between the age of 30-80 with Mild or Mild-to-Moderate ED and controlled Diabetes Mellitus (DM)					
STUDY	Primary: To investigate biochemical markers of neo-angiogenesis in patients before and after PRP injection + SWT					
OBJECTIVES	Secondary: To study efficacy and incidence of adverse events and safety of PRP injection + SWT treatment in men with mild-moderate ED, as measured by IIEF.					
	15 men with Erectile Dysfunction (ED) of organic origin and Diabetes (Type 1 or Type 2), that meet all of the inclusion and none of the exclusion criteria, will be enrolled and will receive PRP+SWT.					

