3.1 Primary Endpoints

- Changes in markers of vasodilation (eNOS, nNOS), neo-angiogenesis (VEGF, CD-31), and systemic markers of endothelial function (EPCs, SDF-1α, and SCF).

3.2 Secondary Endpoints (efficacy):

- Differences in Doppler ultrasound parameters (PSV and EDV) from baseline to 6 months post-therapy.
- Treatment satisfaction as assessed by EDITS questionnaire in all subjects.
- Incidence of Serious Adverse Events experienced up to 6 months post-therapy.

3.3 Exploratory Endpoints:

- Change in IIEF-EF score from baseline to 3 and 6 months post-therapy.
- Percentage of subjects that achieve minimal clinically important difference (MCID) in IIEF-EF from baseline to 3 and 6 months post-therapy.
- Percentage of subjects who either decrease or discontinue use of PDE5i after three months post-therapy

4. Study Location

The study will be funded by the CTSI pilot award (GR019191) and coordinated by the University of Miami (UM), Miller School of Medicine, Desai Sethi Urology Institute. All

study visits will take place in the Department of Urology clinics, (PAC: [name], University of Miami Miller School of medicine, Miami, FL. & Lennar: [name]) PRP preparation and SWT therapy administration will take place in the PAC andrology lab and clinic.

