6.4 Withdrawal Criteria

All subjects who either screen fails, is withdrawn from the study, or has completed all visits should be de-enrolled from the research database within 2 business days, in accordance with university policies (or respective institutional policy).

Subjects may be withdrawn from the study for any of the following reasons:

- a) A subject does not meet the eligibility criteria (the subject will be considered a screen failure).
- b) A subject withdraws consent.
- c) A subject expires during protocol participation from causes other than the study treatment (not due to adverse events).
- d) At the discretion of the principal investigator for issues of non-compliance, or other behavioral factors.

7. Procedures Involved

15 men with Erectile Dysfunction (ED) of organic origin, that meet all of the inclusion and none of the exclusion criteria, will be enrolled to receive PRP+SWT in an open-label fashion.

Autologous PRP injection + SWT therapy. All subjects in this group will receive 2 sessions of autologous PRP penile injection with 28 ± 2 day treatment interval. 5mL of PRP will be injected at each session. Additionally, patients will receive a total of 3600 shocks over a five-week period, starting at initial PRP injection.

7.1 Schedule of Events:

-

The events table for the conduct of this study is shown below:

Table1:

Schedule of Events		Screening			Follow Up				
Time Point		0-30 days	Week 0	Week 1	Week 2	Week 3	Week 4	Month 3	Month 6
Eve	nt	before randomization	Day 0	Day 7 ± 2	Day 14 ± 2	Day 21 ± 2	Day 28 ± 2	Day 90 ± 14	Day 180 ± 14
Infor	med Consent	x							
Dem	ographics	x							
Medi	cal History	x							
Phys	ical Exam	x							
Dopp	oler Ultrasound	x							X
aires	IIEF	x						X	x
tionna	EDITS							X	x
Ques	VAS		x	x	x	x	x		
Labo	ratory Tests*	x							
EPC	-CFUs	X						X	Х
Brac	hial FMD	X						Х	Х
PRP Injection			х				х		
Shockwave Therapy			Х	Х	Х	Х	Х		
Concomitant Medications/Therapy		x	x	х	х	x	x	x	x
Review Adverse Events			х	x	x	x	х	x	x

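### The only analysis plan (section 12.1) compares treatment with control, but the synopsis and the opening of section 7 describe one arm with no control group

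*Combined protocol and SAP*

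**What the plan says.** Section 12.1 is the whole analysis plan. Continuous data go to repeated-measures ANOVA or a Student's t-test "in order to compare differences between the treatment and control groups". Categorical data go to Fisher's "Exact test to determine differences between groups". Significance is judged at 0.05. No endpoint, visit or pairing is named.

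The synopsis gives the design as "Single arm, Open Label, Pilot Trial" and the primary objective as "To investigate biochemical markers of neo-angiogenesis in patients before and after PRP injection + SWT". It says the 15 men "will be enrolled and will receive PRP+SWT". The opening text of section 7 agrees: they "will be enrolled to receive PRP+SWT in an open-label fashion".

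Section 3.1 begins the primary endpoint with "Changes in markers of vasodilation (eNOS, nNOS), neo-angiogenesis (VEGF, CD-31" and goes on to EPCs, SDF-1α and SCF, seven markers in all, with no visit. Section 3.2 does set times for Doppler: "Differences in Doppler ultrasound parameters (PSV and EDV) from baseline to 6 months post-therapy". Section 3.3 sets IIEF-EF change at 3 and 6 months.

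**The concern.** A one-arm trial with a before/after question needs within-subject analyses. The plan states only contrasts that require a second group. If the synopsis design is what will be run, the primary question has neither a stated test nor a stated visit, so both could be settled after the data are seen. For Doppler and IIEF-EF the times are fixed and only the link to a test is missing. For the proportions (MCID responders, serious adverse events) the one named test yields nothing. Because section 12.1 sets a significance level, the plan intends formal testing and should say what is tested.

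**Working it through.** The plan states no power, effect size or sample-size derivation, so there is no figure to reproduce. The check sets passages side by side and tries the stated tests on the stated design.

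**1. Is the design one arm or two?**

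| Place | Design described |
|---|---|
| Synopsis (design, investigation plan) | one open-label arm, 15 men |
| Section 5; section 7 opening text | 15 men, open label; section 7 gives all of them PRP+SWT |
| Section 7.1, schedule column header | screening timed relative to randomisation |
| Section 7.2.13 | a treatment group of randomised patients |
| Section 7.3.2 | randomisation to two parallel groups |
| Section 8.1 | a control arm whose blood is drawn but not processed |
| Section 8.2.1 | a control arm given saline |
| Section 12.1 | treatment versus control |
| Section 13.2 | men randomised to the treatment arm |

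Section 7 is therefore evidence on both sides. The before/after wording of the primary objective stands only in the synopsis; section 2.1 speaks of underlying mechanisms.

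**2. Can the stated tests be run with 15 treated and 0 controls?**

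- Two-sample t-test: the standard error is s × √(1/15 + 1/0), which is undefined.
- Fisher's exact test: with row totals 15 and 0 and k events, only one table is possible. Its probability is C(15,k) × C(0,0) / C(15,k) = 1, so p = 1 for every k. Direct runs at k = 0, 5, 8 and 15 gave p = 1.

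**3. What can 15 men in one arm show?**

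- 0/15 (for example serious adverse events): exact 95% CI upper limit 1 − 0.025^(1/15) = 1 − 0.782 = 21.8%, so 0 to 21.8%.
- 8/15 (for example MCID responders): Clopper-Pearson limits from Beta(8, 8) at 0.025 and Beta(9, 7) at 0.975, giving 26.6% to 78.7%.
- Mean change: 95% CI half-width t(0.975, 14)/√15 = 0.55 SD of the change.

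The counts 0 and 8 are examples, not figures from the documents.

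**4. Primary markers against the schedule.** The endpoint names eNOS, nNOS, VEGF, CD-31, EPCs, SDF-1α and SCF. The schedule of events has one matching row, EPC-CFUs, at screening, Month 3 and Month 6. There is no row for the other six. Section 7.2.10 says plasma is kept for later analysis, without naming a marker.

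**5. Multiplicity.** Seven markers each tested at 0.05, assuming independence: 1 − 0.95^7 = 1 − 0.698 = 30.2%.

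**The case against.** The strongest reply is that the named methods are adequate: repeated-measures ANOVA contains a within-subject factor, and a t-test can be paired. That stands. A reader might infer that the plan names no method able to answer a before/after question, and that would be wrong. What is missing is the link: section 12.1 directs these methods at groups and never at visit or paired change. Fisher's test has no such rescue.

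A reader might also infer that the t-test is unpaired, with a loss of power. Section 12.1 does not say so, and the documents give no correlation between visits, so no such loss can be claimed.

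It could be argued that the trial really has two arms and that section 12.1 is the correct part. The leftover wording in six other places makes that thinkable, but the synopsis, section 5 and the opening of section 7 all describe 15 men in an open-label study, and no allocation ratio or number per group is given. Some text must change under either reading.

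It is also tempting to say that six of the seven markers will not be measured. The documents do not show this, since stored plasma is mentioned. They show only that no sampling for those six is scheduled.

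Finally, this is a 15-man pilot. That limits the consequences, but does not supply an analysis for the primary question.

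**Conclusion.** The point holds, conditional on the single-arm design stated in the synopsis. Section 12.1 then offers no contrast that can be made: the between-group comparisons lack a second group, and Fisher's test gives p = 1 for any count. The primary endpoint has no stated visit, and six of its seven markers have no row in the schedule. The 30.2% family-wise error assumes independent markers and unadjusted tests at 0.05; correlated markers would give a different figure. The documents do not support a wider claim that every change endpoint lacks a visit, because Doppler and IIEF-EF have theirs. Nor does section 7 itself state a before/after objective. The correction should be made before any data are analysed.

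**What to change.** 1. Reconcile the randomisation, control-arm and saline wording in sections 7.1, 7.2.13, 7.3.2, 8.1, 8.2.1, 12.1 and 13.2 with the single-arm design.
2. Rewrite section 12.1 for one arm. For each of the seven primary markers, and for PSV, EDV and IIEF-EF, report the mean within-subject change from baseline with a 95% CI and a paired t-test or Wilcoxon signed-rank test. Name one post-baseline visit as primary for the markers. Any repeated-measures ANOVA over visits is supportive, because its overall visit effect does not test the named contrast.
3. Adjust across the seven markers, for example by Holm (smallest p-value against 0.05/7 = 0.0071), or label their p-values exploratory.
4. Reconcile the seven-marker endpoint with the schedule, which shows sampling for EPC-CFUs only.
5. Replace Fisher's test with exact 95% CIs for the MCID and serious-adverse-event proportions. Summarise EDITS descriptively, as it is not collected at baseline.

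The cost is protocol and analysis-plan wording, plus less favourable p-values if an adjustment is adopted.

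Two related conflicts need separate reconciliation and do not carry this point. The schedule counts follow-up by study day, while section 7.3.3 counts from the final treatment visit. The PDE5i-reduction endpoint in section 3.3 sits beside section 5, where all men are regular users, and section 7.2.14, which requires them to stop for the whole study.
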